6. RECRUITMENT, ENROLMENT AND RANDOMISATION

6.1. Recruitment

Patients will be identified by doctors, research nurses and research midwives. All women undergoing a surgical evacuation of products of conception will be considered for the trial. Their clinical notes will be screened in order to ascertain eligibility. Only a member of the patient's existing clinical care team will have access to patient records in order to identify potential participants and check whether they meet the inclusion criteria or make the initial approach to patients.

All participants will be approached and recruited at a recruiting NHS hospital. A patient facing poster advertising the study will be displayed in clinically appropriate areas within the hospital.

Following a recent survey, 320 surgical evacuations are performed on average per year (60 evacuations under local anaesthetic and 260 under general anaesthetic). We will aim to recruit 90 participants in approximately 6 months.

6.2. Enrolment and Screening

The research team will work closely with the multidisciplinary team responsible for routine patient care. All women undergoing a surgical evacuation of products of conception will be considered for the trial. The trial will be introduced through a comprehensive, evidence-based patient information sheet that will be provided prior to the procedure. Participant information sheets and consent form will be provided to each centre in English and other languages in accordance with standard hospital procedures.

6.3. Randomisation

Randomisation will be provided by a secure online randomisation system at the Birmingham Clinical Trials Unit (BCTU) (available at www.bctu-redcap.bham.ac.uk/SEEU). Unique log-in usernames and passwords will be provided to those who wish to use the online system and who have been delegated the role of randomising participants into the study as detailed on the SEE U Trial Signature and Delegation Log. The online randomisation system will be available 24 hours a day, 7 days a week, apart from short periods of scheduled maintenance. A telephone toll-free randomisation service ([name]) is available Monday to Friday, 09:00 to 17:00 UK time, except for bank holidays and University of Birmingham closed days.

After participant eligibility has been confirmed by a research nurse or doctor and informed consent has been received, the participant can be randomised into the trial. Paper based randomisation notepads will be provided to investigators and may be used to collate the necessary information prior to randomisation. All questions and data items on the

Randomisation Notepad must be answered before a Trial Number can be given. If data items are missing, randomisation will be halted, and the randomisation process restarted in the trial database once the information is available. Only when all eligibility criteria have been provided will a Trial Number be allocated.

Participants will be randomised at the level of the individual in a 1:1 ratio to either surgical evacuation of products of conception with intraoperative ultrasonography or surgical evacuation of products of conception without intraoperative ultrasonography.

Random permuted blocks of variable length will be used to ensure that the staff recruiting participants to the trial cannot reliably predict the next allocation. To ensure balance in the treatment allocation, randomisation will be stratified by the following variables:

- Proposed anaesthesia type (none/local or general);
- Randomising site

Full details of the randomisation specification will be stored in a confidential document at BCTU.

Following randomisation, a confirmatory e-mail will be sent to the randomising clinician, local PI, local Research Nurse and trial co-ordinating office.

Investigators will keep their own study file log, which links patients with their allocated trial number in the SEE U **Patient Recruitment and Identification Log**. The Investigator must maintain this document, which is **not** for submission to the Trials Office. The Investigator will also keep and maintain the SEE U Screening Log which will be kept in the ISF, and should be available to be sent to the Trials Office upon request. The SEE U **Patient Recruitment and Identification Log** and SEE U **Participant Screening/Enrolment Log** should be held in strict confidence.

6.4. Informing the participant's GP

If the participant has agreed, the participant's GP should be notified that they are in the SEE U trial, using the SEE U **GP Letter.**

6.5. Blinding

This will be an open trial design. It will not be possible to blind the surgeon from the use of ultrasound during the surgical management of miscarriage. If the procedure is performed under a general anaesthetic then the patient will be blinded from the intervention, but it will be obvious to the patient that ultrasound is being used if the surgical management of miscarriage is performed using local anaesthetic. Due to staffing restrictions it will not be possible to guarantee that the surgeon performing the hysteroscopy was not involved in the surgical management of miscarriage.

7. TRIAL TREATMENT / INTERVENTION

7.1. Surgical procedure

Surgical evacuation of the uterine cavity for the management of incomplete miscarriage generally involves vacuum aspiration or sharp metal curettage. Vacuum aspiration uses a soft or rigid suction catheter attached to a vacuum source for evacuation of the uterus. It can be used in the office setting without general anaesthesia and can be used with a handheld vacuum syringe (Manual Vacuum Aspiration). This can be done with conscious sedation or with local anaesthetic. Sharp metal curettage is usually performed with regional or general anaesthesia in an operating room. Dilation of the cervix is not usually required in incomplete miscarriage and the metal curette is used to evacuate the contents of the uterine cavity. To maximise recruitment and generalisability the physician will be free to choose the exact method of surgical evacuation and the choice of anaesthetic, although the details of the treatment will be recorded. Serious complications of surgery can include: perforation of the uterus, cervical tears, intra-abdominal trauma, intrauterine adhesions and haemorrhage.

7.2. Intraoperative ultrasound

With intraoperative pelvic ultrasound the clinician is free to follow their usual procedure for evacuation of the contents of the uterine cavity. However, a second person performs a simultaneous abdominal pelvic ultrasound to allow visualisation of the cervix and uterine cavity.

Those performing the ultrasound and the surgeon need to be competent to use the ultrasound safely, as determined by their local hospital competency assessments. Training will be provided by the Chief Investigator on the correct use of ultrasound guidance for both surgeons and assistants in order to ensure the correct technique is used. Clear views of the uterine cavity and cervix are vital to ensure the safety of the procedure. When clear views are not possible due to increased bowel gas or patient adiposity it may be necessary to fill the urinary bladder with warm saline to ensure an acoustic window to improve visualisation of the uterus.

These scans are painless and safe. Unlike X-rays and other imaging tests, they do not use radiation. They have not been found to cause any problems or complications. Once the cavity appears empty on ultrasound the procedure is stopped.

7.3. Drug Interaction or Contraindications

All Rhesus negative women will be offered at least 250IU anti-D irrespective of their allocation. Prophylactic antibiotics will not be used. With the exception of the intraoperative pelvic ultrasound allocation following randomisation, all other aspects of patient management will be as the discretion of the local investigators.

7.4. Accountability Procedures

Surgical evacuation of the uterine cavity is widely performed across the NHS and is regarded as a safe procedure. Details of all procedures conducted will be recorded in the patient's clinical notes, along with their subsequent outcomes. These data will be recorded in the case report forms.

7.5. Cessation of Treatment / Continuation after the Trial

A participant may be withdrawn from trial intervention if it becomes medically necessary in the opinion of the investigator(s) or clinician(s) providing patient care. In the event of such premature treatment cessation, SEE U study personnel will make every effort to obtain and record information about the reasons for discontinuation and any adverse events, and to follow up all safety and efficacy outcomes as appropriate.

8. OUTCOME MEASURES AND STUDY PROCEDURES

8.1. Clinical assessments and procedures

Procedural and baseline information will be collected prospectively during the intervention. Researchers will input the data directly onto a specifically created case report form. Baseline demographic information will include the patient's age, BMI, gestation, parity, if general anaesthesia is to be used, and type of miscarriage. The type of miscarriage included in this trial will be those diagnosed with early embryonic demise which is a delayed or missed miscarriage: The NICE guidance will be followed for the diagnosis of miscarriage (See box 1).

Following randomisation, the surgical procedure for the management of miscarriage will be conducted with or without intraoperative ultrasonography

Two to four weeks later, patients will be contacted to assess whether they have developed an infection after the procedure.

Four to eight weeks after the procedure, patients will undergo a follow-up hysteroscopy in the office setting without general anaesthesia. This is solely to identify if any intrauterine adhesions have formed following the surgical management of miscarriage. This is an important outcome because the prevalence of intrauterine adhesions is underestimated by clinicians and is thought to be related to the number of curette insertions and how vigorously the curettage in performed [18,19]. Two cohort studies reported 8-19% of women had intrauterine adhesions after surgical management of miscarriage [18,19]. Moreover, intrauterine adhesions can lead to menstrual disorders, infertility, pelvic pain and endometriosis.

Box 1. NICE guidance for diagnosis of non-viable intrauterine pregnancy

1.4.5

When performing an ultrasound scan to determine the viability of an intrauterine pregnancy, first look to identify a fetal heartbeat. If there is no visible heartbeat but there is a visible fetal pole, measure the crown–rump length. Only measure the mean gestational sac diameter if the fetal pole is not visible. 1.4.6

If the crown-rump length is less than 7.0 mm with a transvaginal ultrasound scan and there is no visible heartbeat, perform a second scan a minimum of 7 days after the first before making a diagnosis. Further scans may be needed before a diagnosis can be made.

1.4.7

If the crown-rump length is 7.0 mm or more with a transvaginal ultrasound scan and there is no visible heartbeat:

- seek a second opinion on the viability of the pregnancy and/or
- perform a second scan a minimum of 7 days after the first before making a diagnosis.
- 1.4.8

If there is no visible heartbeat when the crown-rump length is measured using a transabdominal ultrasound scan:

- record the size of the crown-rump length and
- perform a second scan a minimum of 14 days after the first before making a diagnosis.

1.4.9

If the mean gestational sac diameter is less than 25.0 mm with a transvaginal ultrasound scan and there is no visible fetal pole, perform a second scan a minimum of 7 days after the first before making a diagnosis. Further scans may be needed before a diagnosis can be made.

1.4.10

If the mean gestational sac diameter is 25.0 mm or more using a transvaginal ultrasound scan and there is no visible fetal pole:

- seek a second opinion on the viability of the pregnancy and/or
- perform a second scan a minimum of 7 days after the first before making a diagnosis.

1.4.11

If there is no visible fetal pole and the mean gestational sac diameter is measured using a transabdominal ultrasound scan:

- record the size of the mean gestational sac diameter and
- perform a second scan a minimum of 14 days after the first before making a diagnosis.
- 1.4.12

Do not use gestational age from the last menstrual period alone to determine whether a fetal heartbeat should be visible.

1.4.13

Inform women that the date of their last menstrual period may not give an accurate representation of gestational age because of variability in the menstrual cycle.

1.4.14

Inform women what to expect while waiting for a repeat scan and that waiting for a repeat scan has no detrimental effects on the outcome of the pregnancy.

8.2. Process outcomes

To obtain estimates for important aspects of the protocol to allow development of a substantive trial, specifically:

- 1. To derive real-time data on the design aspects of the study:
 - I. Proportion of eligible women of those screened: this will be the proportion of patients with miscarriage who are approached.
 - II. Proportion of eligible women randomised: this will be the proportion of eligible patients randomised. A conversion rate of less than 33% will be considered unrepresentative and not sufficient to sustain a large study.
 - III. Attrition rates: what is the follow-up rate at 2 to 4 and 4 to 8 weeks? We would expect follow-up rate to be at least 80%, using various methods of contact.
 - IV. Proportion or women switching treatments: this will be the proportion of women randomised to a treatment that do not receive the assigned treatment.
- 2. To derive a realistic understanding of trial processes, in particular:
 - IV. Ascertain robustness of the data collection process during and after the surgical procedure. We would expect completeness of important miscarriage treatment technique and early complication data to be over 90%.
 - V. Determine the support required in units to ensure successful recruitment
 - VI. Why patients decline participation or withdraw after randomisation. The reasons why women declined should be captured on the screening log. This could allow changes to the protocol to make participation within the trial more acceptable.

8.3. Evaluation of acceptability of processes and intervention for patients and staff

8.3.1. Acceptability and impact on patients

We will explore the acceptability of the intervention to patients and any impacts on their stay in hospital and post-discharge. All patients will be asked to provide feedback on their experiences of taking part in the trial, and how they feel it could have been improved. The patients will be asked for their feedback at their follow-up hysteroscopy appointment.

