2.1. Aims and Objectives

The aim of this pilot study is to assess various aspects of the trial design and management and not to determine the relative effectiveness of intraoperative ultrasound during surgical removal of products of conception. The objectives for the pilot study are: To obtain estimates for important aspects of the protocol to allow development of a substantive trial, specifically:

Process outcomes

- 1. To derive real-time data on the design aspects of the study:
 - I. Proportion of eligible women of those screened.
 - II. Proportion of eligible women randomised.
 - III. Attrition rates (proportion of women followed-up at 2 to 4 and 4 to 8 weeks)
- 2. To derive a realistic understanding of trial processes, in particular:
 - IV. Ascertain robustness of the data collection process during and after the surgical procedure.
 - V. Determine the support required in units to ensure successful recruitment
 - VI. Determine why patients decline participation or withdraw after randomisation.

Evaluation of acceptability to processes and intervention for patients and staff

- 1. Evaluate if outcome measurement tools and processes are acceptable and adequate.
- 2. Acceptability and impact on patients of the interventions.
- 3. Assessment of trial processes, including the choice of outcome measures and impact on staff.

Clinical outcomes

- 1. Derivation of the preliminary data from clinical outcomes measures, in particular intrauterine adhesions at 6 weeks, to inform sample size.
- 2. Evaluate if outcome measurement tools and processes are acceptable and adequate.

The pilot study should enable us to come to one of the following conclusions:

- A substantive study is not feasible.
- A substantive study is feasible with substantial modifications to the trial protocol to improve recruitment, compliance and follow-up.
- A substantive study is feasible with minor modifications to the trial protocol to improve recruitment, compliance and follow-up.
- The substantive study is feasible using the pilot protocol.

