13. STATISTICAL CONSIDERATIONS

13.1. Sample Size

The estimated sample size for the substantive study will be partially informed by the output from this pilot study but will be sufficiently powered to detect a minimally important reduction in rates of the composite measure. This study will aim to enroll 90 women. This number will allow us to measure the recruitment rate with 95% confidence interval (CI) width of approximately 10% if we assume 270 will be eligible over six months recruitment and we recruit a third of these.

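### Patient feedback has one collection point, the 4–8 week hysteroscopy visit, so women who do not attend have no route to give it

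*Protocol*

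**What the plan says.** Section 8.3.1 of the protocol sets the target group as everyone: "All patients will be asked to provide feedback on their experiences of taking part in the trial". It then fixes the occasion: "The patients will be asked for their feedback at their follow-up hysteroscopy appointment". No second occasion or other mode of collection is given.

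The other places that bear on this are:

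- **Section 2.1** makes acceptability of the outcome tools an objective: "Evaluate if outcome measurement tools and processes are acceptable and adequate".
- **Section 8.1** describes the 4–8 week visit as an office hysteroscopy without general anaesthesia and states its purpose: "This is solely to identify if any intrauterine adhesions have formed following the surgical management of miscarriage". It describes the earlier contact in terms of infection only: "Two to four weeks later, patients will be contacted to assess whether they have developed an infection after the procedure".
- **Section 8.2** sets the expected retention at both time points: "We would expect follow-up rate to be at least 80%, using various methods of contact".
- **Section 8.5**, the schedule of assessments, has a row for staff interviews and none for patient feedback.
- **Section 13.1** gives the size: "This study will aim to enroll 90 women".

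**The concern.** The two sentences in Section 8.3.1 agree only if every woman attends the hysteroscopy, and Section 8.2 does not expect that. The hysteroscopy is an added, trial-specific procedure, and its acceptability is among the things the pilot sets out to learn. Section 4.1 admits only women willing to undergo it. A non-attender is therefore someone who agreed in advance and then did not come, and her reasons are especially informative about burden. As written, the plan collects feedback from everyone except this group.

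The pilot has to choose among four conclusions in Section 2.1. Two of them turn on what modifications are needed to improve recruitment, compliance and follow-up. The views of women lost before the hysteroscopy bear directly on that choice. Who is asked, and when, is a matter of data collection. Analysis cannot recover answers that were never sought, and Section 13.3 proposes no imputation.

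**Working it through.** The protocol states no figure for patient feedback. Its one sizing figure, the confidence interval width in Section 13.1, concerns the recruitment rate and plays no part here.

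**Step 1. How many women could have no feedback route.** Inputs: 90 women (Section 13.1) and a follow-up rate f of at least 80% (Section 8.2).

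- Attending at the floor: 0.80 × 90 = 72.
- Not attending: 90 − 72 = 18.

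Eighteen is the most that can be missed if the protocol's expectation is met. At 90% attendance it is 9.

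**Step 2. Whether another provision reaches them.**

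| Provision | What it gives | A woman who silently does not attend |
|---|---|---|
| 2–4 week contact (8.1) | Infection assessment | Contacted, but no feedback is planned |
| Various contact methods (8.2) | Support for the follow-up rate | Not linked to feedback |
| Attrition rate (8.2) | A count | Counted; her views are not recorded |
| Screening log (8.2) | Reasons for declining to take part | Not covered; she was randomised |
| Withdrawal record (8.6) | Date, reason and type of withdrawal | Not covered unless she formally withdraws |
| Schedule (8.5) | No patient feedback row | Not covered |

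None of these gives her a way to provide feedback.

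**Step 3. What this could do to a summary.** The protocol plans no acceptability percentage, so this step is illustrative only. Let a be the favourable share among attenders and b the share among non-attenders.

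- Share in all randomised women = a·f + b·(1 − f).
- With b unknown, it lies between a·f and a·f + (1 − f). The interval has width 1 − f, which is 20 points at f = 0.80 whatever a is.
- Overstatement if only attenders are asked = (1 − f)·(a − b).

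Assume a = 0.90. At f = 0.80 the bounds are 0.90 × 0.80 = 72% and 72% + 20% = 92%. Assume further that b = 0.50:

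| Attendance f | Overstatement (1 − f) × (0.90 − 0.50) |
|---|---|
| 70% | 0.30 × 0.40 = 12 points |
| 80% | 0.20 × 0.40 = 8 points |
| 90% | 0.10 × 0.40 = 4 points |
| 95% | 0.05 × 0.40 = 2 points |

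If b equals a, the overstatement is zero. Only the 90 women and the 80% floor come from the protocol; a, b and the other attendance values are assumptions.

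**The case against.** The strongest case on the other side has five parts.

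- **No acceptability rate is planned.** Section 8.3.1 is exploratory. It defines no favourable rating and no threshold, so a percentage bias describes a statistic the protocol does not intend to report. This stands, and Step 3 is an illustration for that reason.
- **Other evidence bears on the hysteroscopy.** A reader might infer that the pilot could miss an unacceptable hysteroscopy altogether. The documents do not support that. Poor attendance would show in the 4–8 week follow-up rate. Reluctance at entry would show in the proportion randomised, which has a 33% threshold, and in reasons for declining. Section 8.6 also recognises a woman who stops attending trial visits but allows data from standard clinic visits, and it requires her reason to be documented. What remains uncovered is the silent non-attender, a subset of the possible 18 and of unknown size.
- **The concern is weaker for the ultrasound.** Section 6.5 says women under general anaesthetic are blinded to it, so their attendance is unlikely to depend on it. This stands.
- **Late recall is not shown to be a fault.** Section 8.3.1 also covers the period after discharge, which needs a later time point, and nothing in the protocol shows that 4–8 weeks is too late. Recall is not part of this point.
- **No repair reaches everyone.** The 80% expectation applies to the 2–4 week contact too, and some women will refuse all follow-up. This is true, but a second occasion and a remote option still reach women whom the present text leaves out.

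**Conclusion.** The point holds in a limited form. Section 8.3.1 promises feedback from all patients but provides for it only from those who attend the hysteroscopy. With 90 enrolled and the 80% floor just met, up to 18 women have no feedback route. For the hysteroscopy and trial processes, the feedback is conditional on having accepted the procedure and is likely to look more favourable than it would in all randomised women.

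A reader might go further and conclude that acceptability is overstated by a known amount. The protocol does not support this. Upward bias is the expected direction, but some women will miss the visit for reasons unrelated to acceptability, and the size depends on attendance and on non-attenders' views, neither of which is given. The existing process data reduce the gap without closing it. The change is worth making mainly because it is cheap.

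**What to change.** Amend Section 8.3.1, with a matching row in the Section 8.5 schedule, as follows:

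1. Ask the feedback questions on consent, surgery and hospital stay at the 2–4 week contact that already takes place.
2. Keep the questions on the hysteroscopy and on later post-discharge impact for the 4–8 week visit.
3. Offer women who miss that visit, and who still accept contact, the same short questions by telephone or online form, with one more on the reason for not attending.
4. Report the number asked and the number responding out of all randomised women, with attenders and non-attenders shown separately.

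The cost is a wording change, a few minutes on an existing call and a short contact with up to about 18 women. No extra visit or staff is needed. Some women will still not respond, and reporting against all randomised women makes that visible.
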